Aim: To investigate the effects of interval warm-up exercise on EIB severity

Introduction: The *working hypothesis* is that interval warm-up exercise will reduce EIB severity to a similar extent as a SABA and a greater extent than control in obese asthmatic children. Furthermore, we propose that reduction of EIB severity in obese asthmatic children after interval warm-up exercise and/or SABA may be to a lesser extent than in nonobese asthmatic children. The *rationale* behind the proposed research centers on the fact that

EELV will be forced to even lower levels during exercise in an obese asthmatic child creating the potential for increased airway hyperresponsiveness and EIB. In this context, interval warm-up exercise and SABA may improve EIB as it does in nonobese asthmatic children², but obesity-related changes in respiratory function may reduce the effectiveness of interval warm-up exercise and SABA in obese asthmatic children.

Sample size estimation: Our primary variable is maximum % fall in FEV₁ after interval warm-up exercise vs. no-treatment control. Schnall and Landau⁷ reported maximum % fall in FEV₁ after an exercise challenge preceded by interval warm-up of 6.9±5.2% compared to control 23.0±5.2%. Based on these data⁷, we would be able to detect a significant mean reduction in maximum % fall in FEV₁ between the control and interval warm-up at greater than 95% power in 12 nonobese asthmatic children. While effect sizes may be lower in obese asthmatic children, we can detect a maximum 9.9% fall in FEV₁ difference between control and interval warm-up at 80% power with a sample size of 12 obese asthmatic children. A sample size calculation to detect a significant group x treatment interaction was not possible for this aim without preliminary/published data. Nevertheless, testing the effectiveness of interval warm-up exercise on EIB in obese asthmatic children is itself of considerable clinical value and an important clinical outcome in the proposed project.

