Visit 2: Participants will undergo maximal graded cycle ergometry to exhaustion to measure exercise tolerance. Graded cycle ergometry will be performed using 1-min increments of 10W on an electronically braked cycle ergometer (VIAprint™, Vyaire Medical, Yorba Linda, CA). During cycle ergometry, we will measure ventilation and gas exchange to assess minute ventilation (V_E), $\dot{V}O_2$, $\dot{V}CO_2$, respiratory exchange ratio, and ventilatory equivalents for $\dot{V}O_2$ and $\dot{V}CO_2$. During cycle ergometry we will also measure exercise tidal flow-volume loops and participants will perform inspiratory capacity maneuvers by inhaling to TLC every minute to assess end-expiratory lung volume (EELV). Expiratory flow limitation (EFL) will be assessed by comparing overlap of exercise tidal flow-volume loops with the maximal flow-volume loop. For patient safety and to monitor progress during the test, we will also record ratings of perceived breathlessness (RPB: 0–10 scale), ratings of perceived exertion (RPE: 6–20 scale), blood pressure, heart rate, breathing frequency, tidal volume, pulse oximetry (SpO₂), and $P_{ET}CO_2$. $\dot{V}O_{2\max}$ will be confirmed by a supramaximal verification test at 105% of maximal work rate to exhaustion. Maximal exercise capacity will be evidenced by $\dot{V}O_{2\max}$ (highest $\dot{V}O_2$ obtained during maximal or verification test)⁸.

Visit 3: CONTROL VISIT We will ask participants to hold SABA for 8h, corticosteroid for 24h, and long acting asthma medications for 24h prior to the exercise challenge test (ECT) visits. Participants will also be asked to avoid exercise for 24h prior to the visit. We will measure FEV₁ using spirometry, airway function using FOT and FeNO before starting the ECT (see **Fig. 1** for timeline of ECT visits). The ECT will be performed in accordance with the American Thoracic Society guidelines⁵. Target work rate (W) will be calculated as $[(53.76 \times \text{measured FEV}_1) - 11.07]$ ⁵. Work rate will be increased from 60% of target work rate in the first minute, to 75% in the second minute, 90% in the third minute, and 100% in the fourth minute⁹. We will measure HR, SpO₂%, RPB,

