and RPE during 6 minutes of cycling at 80-90% of HR_{max} . We will measure FEV_1 using spirometry and airway function using FOT at 2, 5, 10, 15, and 30min after completing the ECT (see **Fig. 1**). SABA will be administered to any patient with exercise-related respiratory symptoms and the test will be stopped. Spirometry and FOT measurements will be conducted every 5min after SABA administration to determine whether SABA effectively reversed the bronchoconstriction. A decision of whether to exclude the participant from the study will be made after consulting the pediatric pulmonologist.

Visits 4 and 5: ECT will completed 15 min after two randomized conditions: (1) 8 x 30 s interval warm-up and (2) pretreatment with a SABA. We will conduct spirometry and airway function measurements at baseline prior to after interval warm-up exercise or SABA administration. We will also conduct spirometry and airway function measurements at 2, 5, and 10 min after interval warm-up exercise or SABA administration and prior to the ECT to assess bronchodilation or bronchoconstriction resulting from interval warm-up and SABA. FeNO will

only be measured at baseline. ECT will be performed exactly as described in Aim 2. Details regarding interval warm-up and SABA administration are given below.

- Interval warm-up: eight 30 s intervals of cycling at 100% of the target work-rate calculated as $[(53.76 \times \text{measured } FEV_1) - 11.07]^5$. 45 s of active recovery at 20W will be performed between two intervals. The interval warm-up protocol selected for the proposed study was based on published research by Mickleborough *et al*¹⁰ comparing the effects of interval warm-up, SABA and no warm-up on EIB in nonobese asthmatic adults. We will monitor HR and SpO_2 during the test.
- SABA: 4 puffs of Albuterol (90mcg per actuation). Participants will actuate the medication into the spacer, inhale slowly from FRC and hold their breath for 10 s before exhaling. This procedure will be repeated four times with 1 min between actuations.

Statistical analysis plan: Comparisons in maximum % fall in FEV_1 from baseline will be made using a mixed ANOVA (between effect: obese, nonobese; within effect: control, SABA, interval warm-up). Pearson product-moment correlations will be utilized to examine associations between maximum % fall in FEV_1 and airway function (resistance and reactance) and FeNO, measures of body composition, and fat distribution.

[figure not shown]

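### Pre-intervention FEV1 is measured at all three challenge visits but not used as a covariate for maximum % fall, which forgoes a modest gain in precision

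*Combined protocol and SAP*

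**What the plan says.** All places are in the combined protocol and SAP.

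- **Sample size estimation** names the outcome and contrast: "Our primary variable is maximum % fall in FEV₁ after interval warm-up exercise vs. no-treatment control".
- **METHODS, Visit 3 (control visit):** "We will measure FEV₁ using spirometry, airway function using FOT and FeNO before starting the ECT".
- **METHODS, Visits 4 and 5:** "We will conduct spirometry and airway function measurements at baseline". The rest of that sentence is garbled about whether the reading comes before or after the intervention. Further readings follow at 2, 5 and 10 min after warm-up or SABA, before the challenge. FeNO is taken only at baseline.
- **Statistical analysis plan:** "Comparisons in maximum % fall in FEV_1 from baseline will be made using a mixed ANOVA". The between factor is obese or nonobese, and the within factor is control, SABA or interval warm-up. No covariate is named. FeNO appears only in separate Pearson correlations with maximum % fall.
- **Order of visits:** control is always Visit 3. Only warm-up and SABA are randomized, over Visits 4 and 5.

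**The concern.** The three conditions are run on different days. Using each child as their own control removes stable differences between children, but not what changes from day to day. Two such components remain.

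1. **Error in the baseline reading.** The baseline is the reference for % fall, so a reading that is high by chance makes the fall look larger. Each visit has its own reading, so the error does not cancel within the child.
2. **Airway state on the day.** A child whose airways are tighter that day may fall by a different amount.

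The pre-intervention FEV1 carries information on both and cannot be affected by that day's warm-up or SABA, so it is a legitimate covariate. With 12 children per group, some precision may be recoverable at no cost in data. Because control always comes first, chance differences in airway state between the control day and the warm-up day are not balanced by randomization either.

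**Working it through.** **1. The plan's own figures.** Sample size estimation gives "interval warm-up of 6.9±5.2% compared to control 23.0±5.2", so the difference is 23.0 − 6.9 = 16.1 points with SD 5.2 per condition. Alpha is not stated; I assume 0.05 two-sided. For a paired t-test with n = 12, the SD of the difference is 5.2 × √(2(1 − ρ)), which is 7.35 at ρ = 0. The noncentrality is 16.1/7.35 × √12 = 7.6 on 11 df, and power exceeds 99.9%. The same holds up to ρ = 0.7. The stated "greater than 95% power in 12 nonobese asthmatic children" is therefore reproduced.

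The 9.9 points stated for obese children at 80% power does not follow from SD 5.2, which gives 6.54 at ρ = 0. It needs an SD of the difference of about 11.1. That is a separate matter, and even with 11.1 the power for 16.1 points is 99.5%.

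**2. How much baseline error enters the outcome.** To first order, a baseline error of CV% adds an SD of (1 − fall/100) × CV points to % fall. The CV is assumed.

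| CV | Fall 23.0 | Fall 6.9 | Share of 5.2² |
|---|---|---|---|
| 2% | 0.77 × 2 = 1.54 | 0.931 × 2 = 1.86 | 9% to 13% |
| 4% | 0.77 × 4 = 3.08 | 0.931 × 4 = 3.72 | 35% to 51% |

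Not all of this is recoverable, because the covariate also carries the true day-to-day level.

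**3. How much a covariate recovers.** On the log scale, in points, with the worst post-challenge value treated as one reading:

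- baseline B = day + e1
- outcome Y = e1 + c × day + f − e2
- Var(Y) = 2e² + c²d² + f²; Cov(Y,B) = e² + c d²; Var(B) = d² + e²
- adjusted variance = Var(Y) − Cov(Y,B)²/Var(B)

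The documents give none of these inputs. Assumed: day SD d = 3, 5 or 8; measurement SD e = 2, 3 or 4; SD of true fall f = 3, 4.5 or 6; c = 0 or −0.5. That makes 54 combinations.

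| Case (d, e, f, c) | Var(Y) | Cov | Var(B) | Adjusted | Ratio |
|---|---|---|---|---|---|
| 3, 4, 3, 0 (best with c = 0) | 41.0 | 16 | 25 | 30.8 | 0.75 |
| 8, 2, 3, −0.5 (best overall) | 33.0 | −28 | 68 | 21.5 | 0.65 |
| 3, 2, 3, −0.5 (mechanisms cancel) | 19.25 | −0.5 | 13 | 19.23 | 0.999 |

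Over all 54, the ratio runs from 0.65 to 1.00 with median 0.95. In 15 of 54 (28%) the reduction exceeds 10%. The third case shows why the gain is often small: baseline error makes the covariance positive, a larger fall on a tight-airway day makes it negative, and the two can offset each other.

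**4. What the covariate costs.** One model over 24 children and three conditions has (24 − 2) × (3 − 1) = 44 within-child df. Estimating one slope inflates contrast variance by about 43/42 = 1.024. Simulating that model for warm-up vs control within one group of 12 puts the cost of a useless covariate at about 1% to 3%. Net of the 1.024, the ratios run from 0.67 to 1.02 with median 0.97, and 38 of the 54 combinations still gain.

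**The case against.** **The mixed ANOVA is valid as it stands.** This is true. Omitting a covariate is a choice about precision. A reader might infer that the primary contrast is biased or the trial underpowered. The documents support neither: the stated power has ample margin, and nothing shows that airway state differs systematically between visits.

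**Adjustment may lose power with so few children.** In a separate paired analysis of 12 children, one useless covariate raises the detectable difference from 6.54 to 6.96 points, and two raise it to 7.48. The covariate must correlate with the outcome at about 0.34 (one) or 0.49 (two) to break even. These figures are right for that analysis, but they do not carry over to one model of all children and conditions. There, one covariate breaks even at R² = 1 − 42/43 = 0.023, or R of about 0.15.

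**The baseline-error argument depends on a definition the text leaves unclear.** This stands. If % fall at Visits 4 and 5 were taken from a reading after warm-up or SABA, error in the earlier reading would not enter those outcomes. With c = 0 there would be nothing to gain at those visits, and a common slope would fit poorly.

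**% fall already handles baseline.** In part. It removes proportional same-day shifts in FEV1, and the medication and exercise holds limit day-to-day variation. Reading error and day-specific responsiveness remain.

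**FeNO.** A reader might infer that FeNO should be a second covariate because it too is collected. The documents give nothing on its within-child relation to % fall, no calculation here supports it, and the plan already examines it by correlation.

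**Conclusion.** The point holds as a modest, optional improvement. The pre-intervention FEV1 is available at every challenge visit and unused as a covariate, and the fixed control-first order means randomization does not balance the day's airway state for the primary contrast.

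Under the assumed ranges, residual variance falls by a median of about 5%, or about 2.5% in standard error since √0.95 = 0.975. The range is 0% to 35%, and the top needs an extreme combination of inputs. The downside is about 1% to 3% of contrast variance. These sizes rest on assumed variances, on one slope common to all conditions, and on baseline being the pre-intervention reading.

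Any practical value lies where the plan is less certain: the contrast in obese children, where it expects that effects may be smaller, and the group-by-condition interaction, for which it has no sample size calculation. Adjustment deals only with measured airway state. It should not be read as curing the fixed order of control before the other conditions.

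**What to change.** 1. State that baseline for % fall at Visits 4 and 5 is the reading before warm-up or SABA, and repair the garbled sentence in METHODS, Visits 4 and 5.
2. Fit one linear mixed model for maximum % fall over all 24 children and three conditions, with group, condition, group × condition and a random effect for child. Add that visit's pre-intervention FEV1 (% predicted, centred within child) as the single pre-specified covariate. Do not use a reading taken after SABA or warm-up, since the condition affects it.
3. Report the unadjusted contrast alongside.
4. Leave FeNO out of the main model, or use it only in a sensitivity analysis.

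The cost is one model term and a sentence of definition. No new measurement or visit is needed. Pre-specification also prevents a choice of covariates after the data are seen.

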All participants will have no history of smoking, no history or evidence of heart disease, no history of uncontrolled hypertension, no documented and/or diagnosed sleep disorders, no diagnosed diabetes, no metabolic disorders, no history of significant mental illness, no dietary restrictions, no serious health conditions, or no musculoskeletal abnormality that would preclude exercise. Children who have been hospitalized for an asthma exacerbation or who have taken oral glucocorticoids for asthma in the past year and children who have been admitted to an intensive care unit or been intubated because of their asthma in the past five years, will be excluded to reduce the risk of exacerbation during the study³.

BMI criteria: We will study nonobese children with a BMI between the 16th and 84th percentile and obese children with a BMI > 95 th percentile but less than 170% above the 95th percentile and less than an absolute BMI of $40 \text{ kg} \cdot \text{m}^{-2}$. Recently, there has been a shift towards classifying child BMI over the 95th percentile as a percent above the 95% percentile because the statistical procedures used to generate percentile curves are not accurate at the extreme tails of BMI distribution⁴. We have chosen 170% above the 95th percentile as a reasonable cut-off or upper-limit because it will exclude children with an average age and sex specific BMI of approximately $> 40 \text{ kg} \cdot \text{m}^{-2}$ (BMI Range 36 – 43 in boys and 37 – 45 in girls 9 – 12 yr), which roughly corresponds to Class III obesity in adults. Since this BMI percentile range also includes children with a BMI $> 40 \text{ kg} \cdot \text{m}^{-2}$, we will further exclude any children with an absolute BMI $> 40 \text{ kg} \cdot \text{m}^{-2}$.

Lung function criteria: We will study children with 1) FVC $\geq 80\%$ predicted, 2) FEV₁ $\geq 75\%$ predicted, and TLC $\geq 80\%$ predicted, consistent with normal pulmonary function and including participants with mild obstructive airway disease. Since the risk of severe EIB increases in children with moderate or severe obstructive airway disease, children with FEV₁ $< 75\%$ predicted will be excluded from the study⁵. Diagnosis of asthma (i.e., airway responsiveness with reversible obstruction) will be established by spirometry (i.e., improvement of FEV₁ of $\geq 8\%$ after administration of SABA⁶). Children without reversible airway obstruction will also be excluded from the study.

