METHODS: Over five separate visits (1.5 – 2.5 h each), we will measure respiratory function, exercise tolerance, and EIB after an ECT that is preceded by a no-treatment control and two randomized conditions: (1) 8 x 30 s interval warm-up, and (2) pretreatment with a bronchodilator (SABA). Testing that requires physician oversight (e.g., exercise tests) will be conducted at the Sunrise Health and Medical Center (SHMC). Testing that does not require physician oversight, such as plethysmography measurements for lung volumes, will be conducted at UNLV.

Visit 1: We will conduct spirometry and airway resistance measurements (using FOT) before and after SABA (Albuterol 4 puffs, 90mcg per actuation) to assess airway hyperresponsiveness. Participants with an FEV₁ < 75% predicted will be excluded from the study to reduce risk of severe EIB after exercise⁵. Lung volumes (i.e., TLC, FRC, RV) will be measured by plethysmography. Maximal voluntary ventilation (MVV) will be determined from a 10 s test extrapolated to 1 min. Height, weight, circumference measurements (chest, waist, hip, and neck), and BMI percentile will be used to characterize body size and fat distribution.

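### Scored from the pre-treatment reading, % fall in FEV1 counts SABA's resting bronchodilation as protection against exercise, so the comparison with SABA needs a second fall from the last pre-exercise reading

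*Combined protocol and SAP*

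**What the plan says.** The outcome is analysed in one sentence of the Statistical analysis plan: "Comparisons in maximum % fall in FEV_1 from baseline will be made using a mixed ANOVA", with obese versus nonobese as the between-child factor and control, SABA and warm-up as the within-child factor. Sample size estimation names maximum % fall in FEV1, warm-up versus control, as the primary variable, but names no denominator.

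At Visit 3 (control) there is no ambiguity. FEV1 is measured along with "airway function using FOT and FeNO before starting the ECT", and nothing comes between that reading and the exercise challenge test (ECT).

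At Visits 4 and 5 there are two stages of reading before the ECT. The first is described in a garbled sentence: "We will conduct spirometry and airway function measurements at baseline prior to after interval warm-up exercise or SABA administration". The second is a set of readings at 2, 5 and 10 min after the warm-up or SABA, taken "prior to the ECT to assess bronchodilation or bronchoconstriction resulting from interval warm-up and SABA". The ECT follows at 15 min. The analysis plan gives this second set no role.

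Two other parts of the document bear on size. Under Lung function criteria, "Diagnosis of asthma (i.e., airway responsiveness with reversible obstruction) will be established by spirometry", defined as an FEV1 improvement of at least 8% after SABA, and "Children without reversible airway obstruction will also be excluded from the study". The dose at Visit 1 and at the SABA visit is the same: four puffs of albuterol at 90 mcg each.

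**The concern.** The stated hypothesis has two parts: the warm-up reduces exercise-induced bronchoconstriction more than control does, and about as much as SABA does. The second part needs a score that means the same thing in both active conditions.

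SABA opens the airways at rest. Every enrolled child has shown such a response at the study dose, because it is an entry criterion. If the fall after exercise is measured from the reading before SABA, the resting gain is subtracted from the fall. A child whose response to exercise is unchanged then appears partly protected. A warm-up that protects exactly as well as SABA appears inferior to it.

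Using only the last reading before the ECT removes that problem and creates another. If the warm-up itself narrows the airways, the narrowing has already happened by that reading and drops out of the score. A single fall from a single baseline cannot separate the resting change from the response to exercise, whichever baseline is chosen.

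**Working it through.** **Inputs**
- Fall from control: 23.0%. Fall after warm-up: 6.9%. SD 5.2 in each (Sample size estimation).
- SABA gain at rest, r: 8%, the entry minimum (Lung function criteria). Recurrence of this gain at the SABA visit is an assumption. It is varied from 4% to 12%.
- Narrowing caused by the warm-up, d: not in the documents. 5% and 10% are assumed for illustration.

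**The plan's own figure.** The planned difference is 23.0 - 6.9 = 16.1 points. With SD 5.2, n = 12 and an assumed two-sided 5% level, a paired t-test with no correlation between visits (SD of differences 5.2 × √2 = 7.35) has power above 99.99%. The plan's claim of more than 95% in nonobese children is reproduced.

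**Which reading is baseline?** The Visits 4 and 5 text attaches the word to a reading before the condition, introduces the 2, 5 and 10 min readings as additional, and limits FeNO to baseline. All three point to the pre-treatment reading. No sentence ties this to the endpoint.

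**SABA scored from the pre-treatment reading.** Let x be the fall from the pre-ECT level. The lowest FEV1 is (1 + r)(1 - x) of the pre-treatment value, so

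score = 1 - (1 + r)(1 - x), and shift from x = r(1 - x).

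| True fall x | r | Score | Shift (points) |
|---|---|---|---|
| 23.0% (no protection) | 4% | 1 - 1.04 × 0.770 = 19.9% | 3.1 |
| 23.0% | 8% | 1 - 1.08 × 0.770 = 16.8% | 6.2 |
| 23.0% | 12% | 1 - 1.12 × 0.770 = 13.8% | 9.2 |
| 6.9% (same as warm-up) | 4% | 1 - 1.04 × 0.931 = 3.2% | 3.7 |
| 6.9% | 8% | 1 - 1.08 × 0.931 = -0.5% | 7.4 |
| 6.9% | 12% | 1 - 1.12 × 0.931 = -4.3% | 11.2 |

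In the lower three rows the shift is also the gap between SABA and the warm-up, provided that the warm-up leaves resting FEV1 unchanged and so scores 6.9%.

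**Warm-up scored from each reading.** With x = 6.9% from the pre-ECT level and narrowing d, the score from the pre-treatment reading is 1 - (1 - d)(1 - x).

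| d (assumed) | Score, pre-ECT reading | Benefit over control | Score, pre-treatment reading | Benefit over control |
|---|---|---|---|---|
| 5% | 6.9% | 16.1 | 1 - 0.95 × 0.931 = 11.6% | 11.4 |
| 10% | 6.9% | 16.1 | 1 - 0.90 × 0.931 = 16.2% | 6.8 |

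The pre-treatment reading charges the narrowing to the warm-up. The pre-ECT reading hides it.

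**The case against.** The strongest reply is that there is little real ambiguity. The section uses the word baseline for the pre-condition reading, the garbled phrase looks like a slip, and the missing timeline figure may label the reading outright. This largely stands: the gap is an unclear definition with a likely answer. A reader might infer that the primary variable is undefined or contradictory; the documents do not support that.

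A second reply is that the primary contrast is unharmed. Under the likelier reading, SABA's bronchodilation does not enter warm-up versus control, and narrowing caused by the warm-up counts against it. This stands too. A reader might infer that the main result is tilted towards the warm-up. That would need the less likely baseline together with narrowing, and the documents give no size for narrowing.

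A third reply is that counting bronchodilation as part of SABA's benefit is a legitimate choice, and that the extra readings are scheduled precisely to assess resting change. It is a legitimate choice. However, the hypothesis is about the severity of bronchoconstriction after exercise, and the analysis plan never uses those readings. With the single planned score, nobody could tell which part of SABA's advantage came from where.

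Finally, a reader might turn the 7.4-point gap into a probability of a significant result. The documents do not support this. They give no SD for SABA versus warm-up and name no pairwise test of it. An SD worked back from the 9.9-point detectable difference for 12 obese children (about 11.1, paired) does not agree with the stated 5.2.

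**Conclusion.** The concern holds for the comparison with SABA. On the likelier reading of baseline, the plan gives an answer about similarity to SABA in which resting bronchodilation and protection against exercise cannot be told apart. At the 8% entry minimum, the mixing is worth 6.2 points when SABA gives no protection, about 38% of the planned 16.1-point effect (6.2 / 16.1). It is worth 7.4 points when SABA and the warm-up protect equally, and 3.7 to 11.2 points for gains of 4% to 12%.

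These sizes assume that the Visit 1 gain recurs and is present when the ECT starts, that an unchanged response to exercise means the same % fall from the pre-ECT level, and, for the gap against the warm-up, that the warm-up does not move resting FEV1. The planning means are treated as the values of a typical child.

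Warm-up versus control is sound on this baseline. Switching to the pre-ECT reading alone would not be a cure, because it could hide harm from the warm-up.

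**What to change.** Replace the garbled sentence under Visits 4 and 5 with:

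> Baseline is the FEV1 before the warm-up or SABA at Visits 4-5 and before the ECT at Visit 3.

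Add to the Statistical analysis plan:

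> The primary variable, used for warm-up versus control, is the maximum % fall from this baseline after the ECT. For all three conditions, the maximum % fall from the last reading before the ECT is analysed in the same mixed ANOVA, and the change from baseline to that reading is reported. The statement on similarity to SABA is based on both falls.

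At Visit 3 the two readings coincide, so the control score is the same under both definitions. If the two falls disagree on SABA, the reported resting change shows why.

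The cost is one corrected sentence and three added ones. No visit, measurement or child is added, and the sample size does not change. The fix does not create a formal test of similarity, since the plan states no margin for one. A stopping threshold after the warm-up is a separate safety matter and is not needed here.
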